10.6.5.4. Physical Examination

A listing of any new (or worsening) findings will be provided.

10.6.5.5. Clinical Laboratory Test

Descriptive statistics for clinical laboratory values and changes from the baseline values at each visit will be presented by treatment group for each clinical laboratory parameter. Also, the shift-table of change of status from the baseline to the last visit will be presented for each clinical laboratory parameter. Listings will be presented for patients with clinically significant abnormal values.

10.6.5.6. Chest X-ray

Listings will be presented for patients with chest x-ray abnormalities during the trial.

10.6.6. Immunology

10.6.6.1. Anti-Epoetin Antibody

Listings will be presented for patients with anti-epoetin antibodies during the trial.

10.6.7. Determination of the Sample Size and it's Rationale

10.6.7.1. Sample Size

There are two co-primary endpoints in this study; the mean change in hemoglobin level and the mean change in weekly dose per kg body weight from baseline period to the evaluation period. In determining the sample size of studies with co-primary endpoints, generally sample sizes are calculated for each co-primary endpoint and then the larger sample size is adopted (Volker Wizemann et al, 2008).

To achieve 90% power of the mean change in hemoglobin level, a sample size of 126 is required per group. In the case of weekly dose, a sample size of 97 is needed per group. The larger sample size of hemoglobin level (n=126) is chosen for the trial, which is expected to give a overall 80% power for the proof of equivalence. The total number of patients to be enrolled will be 316, including an assumed drop-out/protocol violation rate of 20%.

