2. SYNOPSIS

CLINICAL STUDY SYNOPSIS: Study PG-EPO-Ph3	
Study Number	PG-EPO-Ph3
Study title	A multi-center, multi-national, double-blind, randomized, active-controlled, parallel-group clinical study to assess safety and efficacy of PDA10 (epoetin-alfa) compared to Eprex® in patients with anemia of chronic renal failure
Development Phase	III
Objective	
 • The primary objective is to demonstrate the therapeutic equivalence of PDA10 to Eprex® in patients with end stage renal failure (ESRD) on chronic hemodialysis. The therapeutic equivalence shall be evaluated by the difference between treatment groups in the change in hemoglobin from baseline, while taking into account differences in epoetin dosage. • The secondary objective is to assess the safety and tolerability of PDA10. • The aim of the open label extension phase is to assess the long-term safety and tolerability of PDA10.
Study Design	
 • A multi-center, multi-national, randomized, double-blind, active-controlled, parallel-group clinical trial • Study period: 24 months after IRB approval • Study period per patient: approximately 64 weeks 
 - Titration phase: 12 weeks (in substantiated cases, a prolongation of the titration phase will be allowed up to 20 weeks and the baseline period [observation period] is the last four weeks of the titration phase.) - Maintenance phase: 28 weeks including 4 weeks of the evaluation period (the evaluation period is the last 4 weeks of the maintenance phase.) - Open-label extension phase: 24 weeks
Number of Patients	The planned sample size is 126 per group, which will be expected to give an overall 80% power for the proof of equivalence. The total number of patients to be enrolled will be 316, including an assumed drop-out/protocol violation rate of 20%.

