10.6. STATISTICAL METHODS

10.6.1. General Principles of the Result Analysis

Statistical analyses will be performed using the data analysis software SAS® Version 9.2 or higher.

Statistical testing will be done at alpha=0.05 level, two-sided, without any adjustment for multiple comparisons unless otherwise specified. The p-values will be rounded to 4 decimal places; p-values less than 0.0001 will be presented as “<.0001” in all tables.

Summaries of categorical variables (nominal or ordinal) will include frequency and percentage of patients at each level of response. Continuous variable summaries will include n, mean, median, standard deviation, minimum and maximum values.

The primary efficacy analysis will be based on the PP population.

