10.6.4. Efficacy Assessment

10.6.4.1. Primary Efficacy Variable

Maintenance Phase

From the statistical point of view, the question of therapeutic equivalence will be approached by calculating the upper limit and the lower limit of 95% one-sided confidence interval of the difference between both treatment groups of the primary endpoints:

- mean change in hemoglobin level between the baseline period and the evaluation period
- mean change in weekly dosage per kg body weight between the baseline period and the evaluation period

* The baseline period is the last four weeks of titration phase and the evaluation period is the last four weeks of maintenance phase. Hemoglobin, hematocrit and the dosage of epoetin for the baseline period will be collected at Week -4, Week -2 and Week 0, and those for the evaluation period will be collected at Week 24, Week 26 and Week 28.

To demonstrate the therapeutic equivalence, two one-sided test (TOST) procedures will be used. It decomposes the interval hypothesis into two one-sided parts – $H_0: d < d_L$ and $H_1: d > d_U$, where d is the difference of the mean change in each primary endpoint, d_L is the lower limit of 95% one-sided confidence interval and d_U is the upper limit of 95% one-sided confidence interval. Both of these one-sided intervals will be compared with the pre-defined clinical acceptance ranges for the corresponding parameters (± 0.5 g/dl for hemoglobin and ± 45 IU/kg/week for epoetin dosage, based on the respective reference means). The intervals will be calculated by means of ANCOVA model including treatment group as a factor and study center and baseline value as covariates.

The statistical evaluation of the primary endpoint “mean change in weekly dosage per kg body weight between the baseline period and the evaluation period” will be performed based on the nominal dosage declared on the labels of the pre-filled syringes.

As the dosage of epoetin and the corresponding level of hemoglobin are closely interrelated, a hierarchic test strategy will be used in the present trial. The test on a higher level of hierarchy can only be performed, should the target of the previous level be fulfilled. The overall equivalence statement is consistent with a positive outcome on both levels of hierarchy. Due to this reason, no adjustment of alpha values will be required on the separate levels. The levels of hierarchy will be defined as follows:

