10.6.7.2. Rationale

The primary objective is to demonstrate the therapeutic equivalence of PDA10 to Eprex in patients with end stage renal failure (ESRD) on chronic hemodialysis. The hypotheses of interest are given by

$$H_0 : |\theta_t - \theta_c| \geq \delta \text{ versus } H_1 : |\theta_t - \theta_c| < \delta ,$$

where θ_t = Mean change in hemoglobin level/weekly dose between the baseline period and the evaluation period in the PDA10 group,

θ_c = Mean change in hemoglobin level/weekly dose between the baseline period and the evaluation period in the Eprex group,

and δ = Equivalence margin

It is assumed that the mean change in hemoglobin level/weekly dose for PDA10 group and Eprex group are equal and the standard deviations of the mean change in hemoglobin level and weekly dose are also assumed to be 1.1 g/dL (M. Haag-Weber et al. (2007)) and 86.6 IU/kg (Krivoshiev S. et al. (2010)), respectively (Refer to the table below).

Reference	Treatment	Endpoint	Difference	95% CI	Inferred SD
M. Haag-Weber et al. Scientific discussion EMA:1-26, 2007	HX575 (N=207)	Mean Hb change	0.08	(-0.17, 0.34)	1.1
	Eprex (N=118)				
Krivoshiev S. et al. Advances in Therapy 2010	Epoetin Zeta (N=154)	Mean weekly epoetin dosage over last 4 wks	11.0	(-8.06,29.96)	86.6
	Eprex (N=165)				

In M. Haag-Weber et al. (2007), the equivalence margin of hemoglobin level was ± 0.5 g/dL and “Guideline of Preclinical and clinical evaluation for Biosimilar in Erythropoietin” by FDA also recommends that the appropriate equivalence margin is ± 0.5 g/dL. Therefore equivalence margin of hemoglobin is defined ± 0.5 g/dL. And the equivalence margin of weekly dose is defined ± 45 IU/kg (S. Krivoshiev et al. (2010) and V. Wizemann et al. (2008)).

The subjects are randomly allocated to either PDA10 or Eprex group in the ratio of 1:1. The sample size resulting from hemoglobin level and weekly dose for achieving a 90% power with 5% significance level is given by

[Hemoglobin level]

$$n_t = \frac{(1+1/k)(z_{\alpha} + z_{\beta/2})^2 \sigma^2}{(\delta - |\varepsilon|)^2} = \frac{2 \times (1.645 + 1.96)^2 \times 1.1^2}{0.5^2} = 125.80 \doteq 126 \text{ for the treatment group,}$$

[Weekly dose]

$$n_t = \frac{(1+1/k)(z_{\alpha} + z_{\beta/2})^2 \sigma^2}{(\delta - |\varepsilon|)^2} = \frac{2 \times (1.645 + 1.96)^2 \times 86.6^2}{45^2} = 96.26 \doteq 97 \text{ for the treatment group,}$$

where $\varepsilon = \theta_t - \theta_c = 0$ (mean difference between PDA10 group and Eprex group),

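### The sample-size formula uses 1.96, the value for 95% power, where the text states 90%, so the stated 90% and overall 80% understate power at 126 per group

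*Protocol*

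**What the plan says.** Section 10.6.7.1 sizes each co-primary endpoint separately and takes the larger number. For hemoglobin: "To achieve 90% power of the mean change in hemoglobin level, a sample size of 126 is required per group". For dose: "In the case of weekly dose, a sample size of 97 is needed per group". The synopsis adds: "The planned sample size is 126 per group, which will be expected to give an overall 80% power for the proof of equivalence", and 10.6.7.1 repeats the 80%.

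Section 10.6.7.2 introduces the formula with "The sample size resulting from hemoglobin level and weekly dose for achieving a 90% power with 5% significance level is given by". It is n = 2 (z_alpha + z_beta/2)² SD² / margin², filled in as 1.645 + 1.96 for both endpoints. The assumptions are equal mean changes in the two groups, SDs of 1.1 g/dL and 86.6 IU/kg, and margins of ±0.5 g/dL and ±45 IU/kg.

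The test being powered is in 10.6.4.1: "To demonstrate the therapeutic equivalence, two one-sided test (TOST) procedures will be used", carried out by "calculating the upper limit and the lower limit of 95% one-sided confidence interval of the difference between both treatment groups of the primary endpoints". Both levels of the hierarchy use the same 95% one-sided limits.

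**The concern.** In this formula the first z value carries the significance level and the second carries the power. For 90% power beta is 0.10, beta/2 is 0.05, and z_beta/2 is 1.645. The value 1.96 is z_0.025, which goes with beta = 0.05, that is 95% power. The stated power, the stated significance level and the printed sample size therefore cannot all be right.

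The overall 80% looks wrong for a second reason. It is what results if each endpoint has exactly 90% power (1 − 0.10 − 0.10 = 0.80, or 0.9 × 0.9 = 0.81). But the protocol's own calculation says dose needs only 97 per group, so at 126 dose power must exceed its target.

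What is at stake is the accuracy of the sample-size justification. A reader relying on it would take the trial to have a one-in-five chance of missing equivalence between identical products, when under the protocol's assumptions that chance is about 6%.

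**Working it through.** **Inputs.** From 10.6.7.2: true difference 0, SDs 1.1 g/dL and 86.6 IU/kg, margins 0.5 g/dL and 45 IU/kg, 1:1 allocation, 90% power, 5% level. From 10.6.4.1: two one-sided tests with 95% one-sided limits, so 5% per side and z_alpha = 1.645. All calculations use the normal approximation, as the protocol does.

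**1. Reproducing the printed figures.**
- Hemoglobin: 2 × (1.645 + 1.96)² × 1.1² / 0.5² = 125.80, so 126.
- Dose: 2 × (1.645 + 1.96)² × 86.6² / 45² = 96.26, so 97.

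The multiplication is right. Only the second z value disagrees with the stated target.

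**2. Sample size for the stated 90% at 5% per side.**
- Hemoglobin: 2 × (1.645 + 1.645)² × 1.1² / 0.5² = 104.8, so 105.
- Dose: 2 × (1.645 + 1.645)² × 86.6² / 45² = 80.2, so 81.
- With 20% excluded, 105 / 0.8 = 131.25, so 132 per group and 264 in total, against 158 and 316 planned.

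**3. Power at 126 per group under the planned test.** Power = 2 Φ(margin/SE − 1.645) − 1, with SE = SD × √(2/126).
- Hemoglobin: SE = 0.1386; 0.5/0.1386 = 3.608; power 95.0% (94.9% with t quantiles).
- Dose: SE = 10.91; 45/10.91 = 4.124; power 98.7% (98.6% with t quantiles).
- Both endpoints: at least 0.9504 + 0.9868 − 1 = 93.7% whatever the correlation; 0.9504 × 0.9868 = 93.8% if independent.

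At its own printed size of 97, dose has 95.2% power, not 90%.

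**4. Sensitivity to the assumptions.**
- *Non-zero difference.* Power becomes Φ((margin − d)/SE − 1.645) + Φ((margin + d)/SE − 1.645) − 1. The table in 10.6.7.2 reports differences of 0.08 g/dL and 11.0 IU/kg in the cited studies. For hemoglobin, 0.42/0.1386 = 3.031 and 0.58/0.1386 = 4.185, giving 91.2%. For dose, 34/10.91 = 3.116 and 56/10.91 = 5.133, giving 92.9%. Both: at least 0.912 + 0.929 − 1 = 84.1%.
- *Hemoglobin SD.* The cited interval (−0.17, 0.34) with 207 and 118 patients implies 0.255 / 1.96 / √(1/207 + 1/118) = 1.128, slightly above the rounded 1.1. With 1.128 and zero difference, hemoglobin power is 93.9% and the joint floor is 0.939 + 0.987 − 1 = 92.6%. The dose SD back-calculates to 86.6, as stated.

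**The case against.** The strongest reply is that nothing depends on the slip. It is conservative: 126 evaluable per group exceeds the 105 that 90% power needs, and both stated power figures are too low. Margins, test, type I error, analysis set and decision rule are unchanged. This stands, and it limits the point to a minor correction.

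The overall 80% can also be defended as a floor: with each endpoint at its 90% target, joint power is at least 1 − 0.10 − 0.10 whatever the correlation. As a lower bound it is true. But the protocol gives it as the expected overall power at 126, and as that it is about 14 points too low under the stated assumptions.

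A reader might go further and infer that the alpha of the equivalence test is unclear, because 1.645 + 1.96 also gives 90% power if each side is tested at 2.5%. At 126 that reading yields 90.1% (hemoglobin), 97.0% (dose) and at least 87.0% jointly, so it rescues the 90% but still not the 80%. The protocol does not support it. The printed order puts 1.645 in the z_alpha position, 10.6.7.2 states a 5% level, and the synopsis and both hierarchy levels in 10.6.4.1 specify 95% one-sided limits. The general rule in 10.6.1, "Statistical testing will be done at alpha=0.05 level, two-sided, without any adjustment for multiple comparisons unless otherwise specified", gives way because the primary analysis does specify otherwise. Moving to 97.5% one-sided limits would change the primary decision rule merely to fit a misplaced z value.

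**Conclusion.** The mismatch is real and can be checked entirely from the protocol. In 10.6.7.2 the value for 95% power stands where the text claims 90%, and the wrong labels carry into 10.6.7.1 and the synopsis. Under the planned test the 90% should read about 95% for hemoglobin and about 98.7% for dose, and the overall 80% should read about 94%, with a floor of 93.7%. These figures hold for zero true difference, the assumed SDs and 126 evaluable patients per group. They are not margins of safety to rely on without those conditions: the protocol's own tabulated differences bring them to about 91%, 93% and at least 84%. Severity is minor. The trial is not underpowered against its stated targets, its alpha is settled at 5% per side, and no equivalence conclusion is threatened.

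**What to change.** Keep 126 evaluable per group, 316 enrolled and the 95% one-sided limits.

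In 10.6.7.2, say that 1.96 for z_beta/2 corresponds to 95% power. In 10.6.7.1, 10.6.7.2 and the synopsis, replace the 90% and the overall 80% wherever they appear with the power at 126 per group: about 95% (hemoglobin), about 98.7% (dose) and about 94% overall (floor 93.7%). Describe 97 for dose as the size for 95% power. State in the same place that these figures assume zero true difference and SDs of 1.1 g/dL and 86.6 IU/kg, and give the values under differences of 0.08 g/dL and 11.0 IU/kg: about 91%, about 93% and at least 84%.

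The cost is protocol wording only: no extra patients and no change to the analysis.

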10.6.7.2. Rationale

The primary objective is to demonstrate the therapeutic equivalence of PDA10 to Eprex in patients with end stage renal failure (ESRD) on chronic hemodialysis. The hypotheses of interest are given by

$$H_0 : |\theta_t - \theta_c| \geq \delta \text{ versus } H_1 : |\theta_t - \theta_c| < \delta ,$$

where θ_t = Mean change in hemoglobin level/weekly dose between the baseline period and the evaluation period in the PDA10 group,

θ_c = Mean change in hemoglobin level/weekly dose between the baseline period and the evaluation period in the Eprex group,

and δ = Equivalence margin

It is assumed that the mean change in hemoglobin level/weekly dose for PDA10 group and Eprex group are equal and the standard deviations of the mean change in hemoglobin level and weekly dose are also assumed to be 1.1 g/dL (M. Haag-Weber et al. (2007)) and 86.6 IU/kg (Krivoshiev S. et al. (2010)), respectively (Refer to the table below).

Reference	Treatment	Endpoint	Difference	95% CI	Inferred SD
M. Haag-Weber et al. Scientific discussion EMA:1-26, 2007	HX575 (N=207)	Mean Hb change	0.08	(-0.17, 0.34)	1.1
	Eprex (N=118)				
Krivoshiev S. et al. Advances in Therapy 2010	Epoetin Zeta (N=154)	Mean weekly epoetin dosage over last 4 wks	11.0	(-8.06,29.96)	86.6
	Eprex (N=165)				

In M. Haag-Weber et al. (2007), the equivalence margin of hemoglobin level was ± 0.5 g/dL and “Guideline of Preclinical and clinical evaluation for Biosimilar in Erythropoietin” by FDA also recommends that the appropriate equivalence margin is ± 0.5 g/dL. Therefore equivalence margin of hemoglobin is defined ± 0.5 g/dL. And the equivalence margin of weekly dose is defined ± 45 IU/kg (S. Krivoshiev et al. (2010) and V. Wizemann et al. (2008)).

The subjects are randomly allocated to either PDA10 or Eprex group in the ratio of 1:1. The sample size resulting from hemoglobin level and weekly dose for achieving a 90% power with 5% significance level is given by

[Hemoglobin level]

$$n_t = \frac{(1+1/k)(z_{\alpha} + z_{\beta/2})^2 \sigma^2}{(\delta - |\varepsilon|)^2} = \frac{2 \times (1.645 + 1.96)^2 \times 1.1^2}{0.5^2} = 125.80 \doteq 126 \text{ for the treatment group,}$$

[Weekly dose]

$$n_t = \frac{(1+1/k)(z_{\alpha} + z_{\beta/2})^2 \sigma^2}{(\delta - |\varepsilon|)^2} = \frac{2 \times (1.645 + 1.96)^2 \times 86.6^2}{45^2} = 96.26 \doteq 97 \text{ for the treatment group,}$$

where $\varepsilon = \theta_t - \theta_c = 0$ (mean difference between PDA10 group and Eprex group),

$k = n_c / n_t = 1$ (allocation ratio),

and $n_c = kn_t$ (the number of patients in the control group)

Consequently, the planned sample size to show the therapeutic equivalence between PDA10 and Eprex group is 126 patients per group. Considering that the chance to be excluded from the PP population is 20%, the total number of patients to be enrolled will be 316 (158 per group).

10.6.8. Handling of Dropouts of Missing Data

- Efficacy analysis:

Any missing data due to subject withdrawal during the study is imputed using the LOCF method. Baseline data is not carried forward to impute the missing data.

- Safety analysis:

Safety analysis is performed on observed value only.

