10.6.2.2. Full Analysis Set (FAS) Population

The Full Analysis Set (FAS) Population consists of all patients who were treated more than 4 weeks with randomized study medication and had at least one postbaseline value of the primary endpoints.

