10.6.2.3. Per-Protocol Population

The Per-Protocol Population, a subset of the FAS Population, is defined as all patients who completed the maintenance phase without any major protocol violations. The precise reasons for excluding patients from the Per-Protocol Population will be fully defined and documented before unblinding.

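### LOCF for withdrawals leaves the completers-only primary analysis untouched, but in any supportive analysis that keeps withdrawn patients it is a single imputation whose bias can run either way, most plausibly toward equivalence for dose

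*Protocol*

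**What the plan says.** Protocol section 10.6.8 gives one rule for efficacy data: "Any missing data due to subject withdrawal during the study is imputed using the LOCF method". It sets one limit: "Baseline data is not carried forward to impute the missing data". No other method for missing efficacy data is named.

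Three other provisions decide where that rule can act:

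- Section 10.6.1: "The primary efficacy analysis will be based on the PP population".
- Section 10.6.2.3 defines that population as "all patients who completed the maintenance phase without any major protocol violations".
- Section 10.6.2.2 defines the FAS as "all patients who were treated more than 4 weeks with randomized study medication and had at least one postbaseline value of the primary endpoints".

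The endpoints are changes from the baseline period to the evaluation period, and section 10.6.4.1 states that "those for the evaluation period will be collected at Week 24, Week 26 and Week 28". Equivalence is approached by "calculating the upper limit and the lower limit of 95% one-sided confidence interval of the difference between both treatment groups" and comparing the limits with ±0.5 g/dl for hemoglobin and ±45 IU/kg/week for dose. Both endpoints must succeed.

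**The concern.** Every patient enters maintenance on a stable individual dose of the same reference product, with hemoglobin between 10 and 12 g/dl. If the two products differ in potency, the difference has to develop after the switch. A patient who leaves at Week 6 or Week 10 contributes a value from that time, and LOCF writes it into Weeks 24 to 28.

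This matters most for dose. Section 10.2 explains that titration masks efficacy differences in hemoglobin, which is why dose is co-primary. Dose moves slowly: section 10.4.4 has it reviewed every four weeks and changed by one nominal 25% step, and a note to the schedule in section 10.5.5.1 limits increases to one per four weeks. An early leaver has had one or two dose decisions, and a temporarily withheld dose could also be carried forward.

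In an equivalence trial, an imputation that shrinks the difference favours the claim being tested. The imputed values are also analysed as if observed. The per-protocol analysis drops all withdrawals, so an analysis that keeps them is the natural check on it, and LOCF makes that check unreliable.

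**Working it through.** **Where the rule acts.** The per-protocol population requires completion of maintenance. A patient who withdraws during maintenance is therefore outside it, and no value missing through withdrawal is left to impute. The error of the primary test at the margin stays at 5.0%. The rule has content only for an analysis that includes withdrawn patients, and the FAS is the only defined efficacy population that can hold them.

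**The plan's own figures.** The Protocol gives no figure for the effect of LOCF. The sample size used below reproduces from section 10.6.7:

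- Hemoglobin: 2 × (1.645 + 1.96)² × 1.1² / 0.5² = 125.80, so 126 per group.
- Dose: 2 × (1.645 + 1.96)² × 86.6² / 45² = 96.26, so 97 per group.
- Enrolment: 126 / 0.8 = 157.5, so 158 per group and 316 in total.

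**Inputs from the Protocol.** Margins M of 0.5 g/dl and 45 IU/kg/week; SDs of 1.1 and 86.6; 5% per side; 158 per group.

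**Assumed inputs.** A true final difference equal to M; all 158 per group in the FAS; SD unchanged by imputation; the same share d withdrawn in each arm; and carried values that show a fraction f of the final difference. With withdrawals spread evenly over Weeks 4 to 24 (mean Week 14) and linear growth to Week 28, f = 14/28 = 0.5.

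**Formulas.**

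- Expected difference after LOCF: D = M × [1 − d(1 − f)]
- Standard error: SE = SD × √(2/158), which is 0.124 for hemoglobin and 9.74 for dose
- Probability of wrongly declaring equivalence: Φ((M − D)/SE − 1.645), because the opposite one-sided test passes almost surely

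Worked case, hemoglobin, d = 0.20, f = 0.5: D = 0.5 × 0.90 = 0.45; (0.5 − 0.45)/0.124 = 0.404; Φ(0.404 − 1.645) = 0.107.

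| Endpoint | d | f | D | One-sided error |
|---|---|---|---|---|
| Hemoglobin | 10% | 0.5 | 0.475 | 7.5% |
| Hemoglobin | 20% | 0.5 | 0.45 | 10.7% |
| Hemoglobin | 20% | 1 | 0.50 | 5.0% |
| Hemoglobin | 20% | 1.5 | 0.55 | 2.0% |
| Dose | 10% | 0.5 | 42.75 | 7.9% |
| Dose | 20% | 0.5 | 40.5 | 11.8% |
| Dose | 20% | 1 | 45 | 5.0% |
| Dose | 20% | 1.5 | 49.5 | 1.8% |

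If the hemoglobin difference is complete by Week 16, f = (12/20) × (10/16) + (8/20) × 1 = 0.775, and the error at 20% withdrawals is 7.2%.

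**Unequal withdrawal.** Suppose the products are truly equal, 20% withdraw on PDA10 and 10% on Eprex, and carried hemoglobin is 1 g/dl low. LOCF then creates a spurious difference of 0.20 × (−1) − 0.10 × (−1) = −0.1 g/dl. Power falls from 98.3% to 94.3%. Here the rule works against equivalence.

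**The case against.** A reader might infer that LOCF tilts the trial's equivalence decision toward success. The documents do not support that: the decision rests on completers, and no section says equivalence is concluded from the FAS. Section 10.6.3 assigns the FAS to demographic and baseline summaries, and section 10.6.4.1 sets out the two one-sided tests without naming it. A supportive FAS analysis is a reasonable inference, but the errors above belong to a decision rule that the Protocol does not state.

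A reader might also infer that LOCF always pulls the arms together. That needs f below 1 and similar withdrawal in both arms. For hemoglobin the Protocol gives a reason to doubt it: by section 10.2, titration dampens hemoglobin differences, so an early gap may later be removed and LOCF would carry the larger one. Lack of efficacy is a listed reason for discontinuation (section 10.3.4), and withdrawal for it may be unequal.

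Three further limits stand:

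- The planned 20% covers drop-outs and protocol violations together, so it is only an upper bound on withdrawals.
- The bar on carrying baseline forward and the FAS requirement of more than 4 weeks' treatment exclude the very earliest values.
- Replacing a three-visit mean with one carried visit may add variance, which works against equivalence; the calculation holds the SD fixed.

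Sensitivity analyses are commonly left to the statistical analysis plan, which is not shown, so their absence is no fault. What survives is narrower: section 10.6.8 itself fixes LOCF as the method, and that choice is poor for the one purpose it can serve.

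**Conclusion.** The point holds as a modest, inexpensive improvement. The primary per-protocol result is unaffected. In a supportive analysis that includes withdrawn patients, LOCF is a single imputation treated as observed data, with bias of uncertain direction: plausibly toward equivalence for dose, either way for hemoglobin.

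The 10% withdrawal case, with errors of about 7.5% and 7.9%, is a fairer central illustration than the 20% bound. All these errors rest on the assumed withdrawal share, the assumed f, equal withdrawal, an unchanged SD and 158 per group; none is a property of the trial as planned. The fall to about 2% under f = 1.5 shows that even the sign depends on those assumptions. That uncertainty is itself a reason not to use LOCF as the check on a completers-only result.

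**What to change.** In section 10.6.8, for efficacy analyses that include withdrawn patients, replace LOCF with one of these:

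- a mixed model for repeated measures on the two-weekly hemoglobin and dose values, with treatment, visit, treatment-by-visit, centre and baseline, estimating the treatment difference averaged over Weeks 24, 26 and 28; or
- multiple imputation of the missing visits, followed by the planned ANCOVA.

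If multiple imputation is chosen, a sensitivity analysis that shifts the imputed PDA10 values toward the equivalence margin may be added. It cannot be attached to the mixed model, which produces no imputed values. The section should also say that the rule does not apply to the per-protocol analysis.

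Sections 10.5.2.1 and 10.5.2.2 already have hemoglobin and dose recorded every two weeks, so no new data are needed. The cost is a wording change, some programming and possibly a slightly wider interval than under LOCF.
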